6.8.2 Timing

AEs noted at Screening through Day 1 and prior to initial study drug administration are pre-existing medical conditions and part of medical history. AEs occurring after study drug administration are treatment emergent AEs.

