6.4 HANDLING OF MISSING VALUES AND OUTLIERS

Because of subject privacy limitations, birth dates may only be reported by month and year in certain locations. Where the specific birth day is not available, the day of month will be imputed as the 15th.

For the primary endpoint in the ITT population, missing height at 12 months will be imputed from the last available height. This imputation assumes no growth after the last available measurement observed at study exit. This is an extremely conservative approach. For example, a █ year old █ subject who discontinued at month 6 with annualized HV of 6 cm/yr (Day 1 height of █ cm and Month 6 height of █) will have the height at 12 months imputed to █ cm, resulting in an annual HV of 3 cm/yr.

For the sensitivity analysis of the effect of missing data on the primary endpoint, height velocity at Month 12, a tipping point approach will be used. The missing data will be imputed as follows:

For the control group:

1. All subjects to the control group mean (calculated without subjects missing endpoint)
2. 50% to the group mean, 50% to the HV associated with each subjects last reported height (no additional gain in height)
3. Each subject's HV imputed based on its own last reported height

For the somavaratan group:

1. All subjects to the somavaratan group mean (calculated without subjects missing endpoint)
2. 50% to the group mean, 50% to the HV associated with each subjects last reported height (no additional gain in height)
3. Each subject's HV based on its own last reported height
4. Each subject imputed to HV based on last reported height, minus 1 cm.
5. Each subject imputed to HV based on last reported height, minus 2 cm (the non-inferiority margin, to avoid imputing to a common mean).

The reduction of the imputed HV by -1 and -2 cm will be limited to a minimum 0 HV, as negative HV is not possible. This will result in a total of 15 comparisons which should cover the range of plausible results for the subjects who are not able to provide Month 12 height velocity, and accounts for combinations where the somavaratan drop outs will have worse outcomes than drop outs in the control group (e.g., control group imputation 1 versus somavaratan imputations 2 to 5).

No imputations will be considered for the PP populations.

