All data collected under this protocol will be included in the assessment of safety. Any AEs missing the relationship to study treatment after repeated query attempts will be assigned as "unknown." Missing or incomplete start dates will be imputed to the date of first dose. Outliers that may have undue influence on the analysis and results will be discussed, but the

results will not be based on any exclusion. No other imputation is planned for the safety population.

Based on the validated assay performed at the central laboratory, the IGF-I values have a lower limit of quantitation (LLOQ) of 16.0 ng/mL and a lower limit of detection (LLOD) of 2.5 ng/mL. As subjects are expected to have growth hormone deficiency, IGF-I values may occasionally fall below the LLOQ. In these cases, the IGF-I value will be assigned to the value midway between the LLOQ and the LLOD, which is 9.25 ng/mL.

Adjustments to the safety laboratory data (blood chemistry, hematology) and IGFBP-3 due to values being below a quantifiable level will be made to indicate a value as one-hundredth (0.01) less than or higher than the limit value (e.g. < 5.0 will be adjusted and summarized as 4.99, > 12.5 will be adjusted and summarized as 12.51).

Adjustments to the PK data due to missing values or for values being below a quantifiable level may be performed, but those will be described in a separate PK report.

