Relationship and severity of adverse events will be summarized (subject count, % of subjects) for each treatment group. For these summaries, multiple occurrences of an event within a subject will be classified as a single observation with the strongest relationship and maximum severity ratings. In addition, frequency tables of all reported events with each associated relationship and severity will be presented.

A tabulation of the incidence of all Grade 3 and 4 treatment-emergent adverse events will be displayed, overall and those related to study drug. Furthermore, a tabulation of the incidence of all treatment-emergent injection site adverse events will be created including, but not limited to, events such as pain/tenderness, erythema, lipoatrophy, stinging, burning, itching, etc. A listing of the treatment-emergent injection site adverse events will supplement the tabulation and will contain dosing information including but not limited to, onset time since last dose, relationship to study drug, dose, grade, injection location, injection volume, number of injections received per dosing event, and duration.

Moreover, a listing of instances of headache reported as an adverse event will be presented which will include information about the event such as, but not limited to, onset time since last dose, relationship to study drug, dose, grade, and duration.

Serious Adverse Events (SAE) are defined as those events that are life threatening, require hospitalization or prolong existing hospitalization; or cause disability, incapacity, or death; or require intervention to prevent such outcomes. These events will be classified as SAEs by the Investigator and appropriate medical review and will be summarized by treatment group, as well as total subjects exposed.

A listing of SAE data will be provided to supplement the tabulated results.

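### SAP 6.4 moves every partly dated adverse event to the first-dose date even when the month or year is known, which falsifies the planned onset and duration fields for those events

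*SAP*

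**What the plan says.** The safety paragraph of SAP 6.4 states: "Missing or incomplete start dates will be imputed to the date of first dose". It makes no distinction between a date that is wholly absent and one that lacks only the day, and it adds: "No other imputation is planned for the safety population". No separate partial-date rule follows. The sentence does not name adverse events, but it comes directly after the rule on missing adverse-event causality, so I read it as applying to them.

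SAP 6.13.1 plans a listing of injection-site events that "will contain dosing information including but not limited to, onset time since last dose", and the fields run on to duration. The headache listing has the same two fields. Both are derived from the start date.

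On treatment-emergent status, SAP 6.13.1 counts findings after the first administration, and also a rise in severity or frequency of a condition present at enrolment. Protocol 6.8.2 sends earlier events elsewhere: "AEs noted at Screening through Day 1 and prior to initial study drug administration are pre-existing medical conditions".

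SAP 6.4 treats partial birth dates differently: "Where the specific birth day is not available, the day of month will be imputed as the 15th". There the known month and year are kept.

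**The concern.** The rule discards information the site has recorded. An injection-site event noted as starting in a known month late in the year, with only the day missing, is analysed as if it began on Day 1.

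The affected fields matter in this trial. Protocol 1.1.3 names lipoatrophy as a safety signal and rates it low risk partly because preliminary data suggest it is transient in most cases, while recent cases need more follow-up. Duration is the quantity that bears on that judgement, and the rule inflates it.

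The distortion also differs by arm. Setting onset to the first-dose date makes the time since last dose zero. That is nearly right under daily rhGH. Under a 15-day somavaratan schedule it would falsely tie events to the injection.

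Partial dates are plausible. Protocol 6.8.1 collects adverse events at clinic visits, and after Month 1 the visits are two to three months apart.

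**Working it through.** The plan gives no figure to reproduce, so the check is a reading of the rule followed by date arithmetic.

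**Inputs from the documents.** Incomplete start dates go to first dose (SAP 6.4). Somavaratan is given every 15 days, window ± 2 days, with 24 assigned doses (Protocol 5.2, Table 1).

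**Assumptions, not in the documents.** First dose is on 20 January 2016, doses are exactly 15 days apart, and the onset month is known but the day is missing. The derived listing fields use the imputed date.

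**Formulas.**
- Error under the SAP rule = true onset − first-dose date.
- Error if the month is kept = true onset − first day of that month (or − first-dose date if it is the first-dose month).

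| Known onset month | Error, SAP rule (days) | Error, month kept (days) |
|---|---|---|
| April 2016 | 72 to 101 | 0 to 29 |
| July 2016 | 163 to 193 | 0 to 30 |
| October 2016 | 255 to 285 | 0 to 30 |

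For October, 20 January to 1 October is 255 days, and 30 more days reach 31 October, giving 285. With a known stop date, duration is overstated by the same number of days. In the first-dose month both rules give the same date.

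**Average size.** If onsets were uniform over days 0 to 364, the mean overstatement would be (0 + 1 + … + 364)/365 = 182 days per imputed event.

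**Time since last dose.** Under the SAP rule it is 0 for every imputed event. The true value on a 15-day schedule lies between 0 and 14 days, or up to about 16 if a dose is given 2 days late (15 + 2 − 1). Keeping the month does not fully recover this field, because a month of about 30 days spans two 15-day intervals. It does restore the event to the right part of the year.

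**Year-only dates.** If only 2016 is known, first dose is still the earliest admissible date. The true onset could be as late as 31 December 2016, which is 346 days later. The 30-day bound does not apply to such dates.

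**Treatment-emergent status.**
1. True onset after first dose: the imputed date is the first-dose date. If a start on that date counts as after first administration, the event correctly stays treatment-emergent.
2. Known month before first dose, for example December 2015: the start is moved 20 to 50 days later (31 December or 1 December to 20 January), and the event becomes treatment-emergent, against Protocol 6.8.2.
3. If 'after' is read strictly as a later date, every event imputed to first dose would lose treatment-emergent status. The SAP does not say which reading applies.

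**The case against.** The best defence is that imputing to first dose is conservative where it counts. An event that began after dosing remains treatment-emergent, and the preferred-term and organ-class tables count each subject once per term and use the start date for nothing else. No time-to-onset or duration analysis is planned, and Protocol 9.1 plans no formal safety tests. The onset and duration fields sit in listings. Pre-dose events should be in medical history under Protocol 6.8.2, and the adverse-event row of both schedules begins at Day 1, so a pre-dose record in the adverse-event data is already misfiled. Partial dates may also be few, since Protocol 10.7 requires missing data to be explained and Protocol 10.6 provides for source verification.

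Most of this stands, and it limits the point to the listings and to partly dated pre-dose records. It does not rescue the rule, because nothing in the SAP confines the imputed date to treatment-emergent status. A programmer following SAP 6.4 would carry it into the derived fields.

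Two stronger readings should not be drawn:
- A reader might infer that treatment-emergent counts are wrong in general. On the ordinary reading they are not, for the reason just given.
- A reader might infer that events with missing causality vanish from the related tables, because SAP 6.4 says "Any AEs missing the relationship to study treatment after repeated query attempts will be assigned as" unknown, and SAP 6.13.1 has repeated events "classified as a single observation with the strongest relationship and maximum severity ratings". The documents do not say this. All safety data are retained, and SAP 6.13.1 also plans frequency tables of all reported events by relationship. The SAP simply does not define related or rank the unknown category. That is a missing detail, not an exclusion.

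**Conclusion.** The concern holds for partial dates. As written, SAP 6.4 overwrites a known month or year. For partly dated injection-site and headache events it gives wrong values for time since last dose and duration. The onset date is off by 255 to 285 days for an onset about nine months in, against at most about 30 days if the known month is kept. It can also make a partly dated event known to precede first dose treatment-emergent.

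This rests on three things: that the sentence covers adverse events, that the derived fields use the imputed date, and the illustrative first-dose date. Another calendar would shift the figures only slightly. How many events are affected cannot be judged, because the documents give no number of partial dates. Efficacy conclusions are untouched. It is a defect in a stated rule that is worth correcting before database lock.

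**What to change.** Replace the sentence in SAP 6.4 with a rule that imputes only the missing parts. Use the earliest date consistent with the known parts, but not before first dose when those parts allow a start on or after it:

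- Month known and the same as the first-dose month, or only the year known and the same as the first-dose year: first-dose date.
- Later month known: first day of that month.
- Only a later year known: 1 January of that year.
- Known month or year, or a stop date, before first dose: not treatment-emergent, unless the event is recorded as increasing in severity or frequency after first dose. The exception is needed because SAP 6.13.1 counts such worsening.
- Fully missing: first-dose date, for treatment-emergent status only, and flagged.

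State that a start imputed to the first-dose date counts as treatment-emergent. Leave fully missing and year-only dates out of the onset and duration displays. It is also sensible to flag dates with an imputed day in the two listings, since time since last dose remains uncertain within the dosing interval.

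The cost is a few lines of SAP text and a standard date macro. No new data are needed and the primary analysis does not change.

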6.5 INTERIM ANALYSES, FINAL ANALYSES, AND UNBLINDING

This is an unblinded study; however, Versartis, Inc. and Investigators will be blinded to the aggregate height velocity data during the trial.

Sample size re-estimation will be conducted by an independent statistical consulting group not directly affiliated with the study. This group will use the observed variance in height velocity to determine if *a priori* assumptions are valid, and will notify the sponsor if the sample size needs to be increased (up to 136 total subjects) to ensure appropriate statistical power.

6.5.1 Safety Reviews

A Data and Safety Monitoring Board (DSMB) meeting will be utilized for the Phase 3 study. A DSMB meeting will be held when a minimum of 50 subjects have completed 6 months of active treatment. All available safety, PD, and immunogenicity data will be provided to DSMB members. DSMB members will review data for any potential risk to subjects and determine if any protocol-specified stopping criteria have been met.

6.5.2 Stopping Rules

The Stopping Criteria for individual subjects include:

- The Principal Investigator and/or Medical Monitor conclude it is unsafe for the subject to continue.
- A new diagnosis of a significant medical condition or initiation of a new treatment if such condition or new treatment can influence the response to study drug (e.g., diabetes, renal failure).
- Individual subjects with a change in HT-SDS ≤ 0 in the past 6 months may be withdrawn from treatment at the discretion of the PI and Medical Monitor.
- For individual subjects with 2 consecutive IGF-I SDS ≥ 3.0 , the PI and Medical Monitor will determine if the subject may proceed with a dose reduction or be removed from the study.

The Stopping Criteria for the somavaratan treatment arm include:

- The determination is made that it is unsafe to continue because of unexpected adverse events.
- A high frequency or unusual severity of expected events such as intracranial hypertension (IH), slipped capital femoral epiphyses (SCFE), progression of scoliosis or other.

6.6 ADJUSTMENT FOR MULTIPLE COMPARISONS

Multiple comparisons of key endpoints are not planned. Any additional comparisons will be for exploratory purposes and definition of a significance level will not be done.

6.7 POOLING OF SITES

Because of the relatively small sample size for each treatment group, all sites will be pooled into one of two Regions: North America and Europe (Rest of World - ROW).

6.8 EXTENT OF EXPOSURE AND TREATMENT COMPLIANCE

Administration of all somavaratan or daily rhGH doses will be performed by health care professionals or parent/guardian. The time, date, dose volume and site of administration will be recorded directly into a study-specific electronic patient-reported outcome (ePRO) solution. Compliance will be summarized and listed, and will be used to determine the Per Protocol population.

6.9 SUBJECT DISPOSITION

The number of subjects enrolled, treated, and discontinued before study end will be summarized by count and percentage for each treatment group.

6.10 DEMOGRAPHIC AND BASELINE CHARACTERISTICS

Demographic and Baseline characteristics will be presented for all subjects and for each analysis population as total enrolled and by treatment group. Gender, race, and ethnicity will be summarized by count and percentage. Age, height, height SDS, body weight, BMI, bone age, IGF-I, IGF-I SDS and IGF-BP3 will be presented with numeric descriptive statistics. Pubertal staging will be summarized by count and percentage for pubic hair and breast development and with numeric descriptive statistics for testicular volume. In addition, age will be summarized into two quantiles using the median.

The subject's age is calculated as the number of years from the subject's date of birth to the date the Informed Consent signed (because of privacy limitation at some sites, the date of birth may only be collected as month and year, and in these cases the date will be imputed as the 15th):

$$\text{Age} = [\text{Date Informed Consent Signed} - \text{Date of Birth}] / 365.25$$

Other Demographic and Baseline characteristics to be summarized with numeric descriptive statistics, where available, are maternal and paternal heights, birth weights, lengths, and

gestational ages, prior height velocities, growth hormone stimulation tests results, and adrenal function tests results.

Demographic and Baseline Characteristics will be summarized for the ITT, PP, and safety populations, should these populations be different.

6.11 EFFICACY ANALYSES

The primary efficacy analyses will be done using the All Randomized population, and will also be done using the mITT and PP populations.

6.11.1 Primary Efficacy Endpoint

Annual height velocity will be calculated using the formula below:

$$\begin{aligned} \text{Height Velocity} \left(\frac{\text{cm}}{\text{year}} \right) \\ = \left[\frac{\text{Month X Height (cm)} - \text{Baseline Height (cm)}}{\text{Month X date} - \text{Baseline date}} \right] * 365.25 \end{aligned}$$

The primary analysis will be the comparison of the annual height velocity between somavaratan and daily rhGH, with null hypothesis that the difference is less than or equal to -2 cm/year, the non-inferiority margin. An Analysis of Covariance (ANCOVA) model will be used to determine the adjusted (least squares) means and SE to determine the confidence interval (CI) of the difference. The model fixed effects are treatment group, region and gender, with baseline age, baseline IGF-I SDS, and baseline height as covariates. The ANCOVA is used to adjust for the influence of these covariates, and not to determine if these covariates themselves are statistically significant factors. A reduced model removing covariates with $p > 0.10$ may also be considered for exploratory purposes. The randomization stratification should result in balance between the two treatments in terms of the factors. Levene's will be used to determine if the variances is equal between the two treatment groups. If there is evidence of unequal variance, a Welch test on the treatment main effects will be performed with null hypothesis of somavaratan HV - daily rGH HV ≤ -2 cm. Rejection of this null hypothesis will be evidence of non-inferiority of somavaratan to daily rGH.

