1. INTRODUCTION/BACKGROUND

This statistical analysis plan (SAP) describes the data analysis specifications for Protocol 14VR4 entitled “Comparison of Somavaratan (VRS-317), a Long-acting Human Growth Hormone, to Daily rhGH in a Phase 3, Randomized, One-year, Open-label, Multi-center, Non-inferiority Trial in Pre-pubertal Children with Growth Hormone Deficiency,” Version 4, 5 April 2017.

This SAP follows the International Conference on Harmonisation (ICH) Guidelines E3 and E9. All statistical analyses will be performed using SAS[®], Version 9.4 or higher. In cases in which the analyses in this SAP differ from those in the study protocol, the analyses in the SAP supersede those in the protocol. Should differences exist, these will be described in Section 6.2 of this document.

This protocol is a randomized, multi-center, open-label, non-inferiority study for pre-pubertal naïve to treatment children with growth hormone deficiency (GHD). Subjects will be randomized to receive 3.5 mg/kg somavaratan twice-monthly or daily treatment with rhGH. Safety and efficacy of these treatments over the course of one year will be evaluated along with changes in pharmacodynamic responses (IGF-I, IGF binding protein-3 (IGFBP-3), growth hormone binding protein (GHBP) and acid labile subunit (ALS)), bone age, weight, body mass index (BMI), height standard deviation scores (HT-SDS), and anti-drug antibody (ADA) responses.

Somavaratan is a fusion protein consisting of recombinant human growth hormone (rhGH) and two sequences (XTEN) of hydrophilic amino acids, designed to maintain active drug levels for a longer period of time than currently available therapies. It is being developed for treatment of GHD in adults and children and as a long-acting alternative to daily rhGH injections, which is currently the only approved treatment in the United States for adults and children with growth hormone deficiency.

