3.5 SAMPLE SIZE CALCULATION/JUSTIFICATION

Sample size estimates are derived from considerations for non-inferiority testing of twice monthly somavaratan versus daily rhGH. The somavaratan arm will be tested against daily rhGH using a one-sided test procedure. Assuming a 3:1 somavaratan to daily rhGH subject ratio, a standard deviation of ≤ 3.0 cm/yr in annual height velocity, an alpha of 0.05 (one-tailed 0.025) and a non-inferiority limit for difference in mean height velocity of 2.0 cm/yr, a total of 76 subjects are required: 57 for the somavaratan dosing arm and 19 for the daily rhGH arm. The total number of planned subjects is 84 (76 plus 8 for potential drop-outs). An independent statistical consulting group will conduct sample size re-estimation using the observed variance in height velocity to determine if *a priori* assumptions were valid and notify Versartis, Inc. if the total sample size should be increased to ensure statistical analyses with adequate power. Assuming the SD (standard deviation) is not greater than 3.5, the sample size should be no greater than 136 subjects.

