5.3 COVARIATES

The adjusted (least squares) mean and SE (standard error) from an analysis of covariance will be used to determine non-inferiority. The ANCOVA model will include treatment group, region and gender as fixed effects, with baseline age and baseline IGF-I SDS as covariates. Baseline height may also be included as a covariate if found to be significant at $p < 0.10$. Other covariates may be considered for exploratory purposes.

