6.2 CHANGES FROM PROTOCOL SPECIFIED ANALYSES

Changes to the protocol may result in changes to the planned analyses, and may change the defined analysis endpoints and methods. Any changes to analysis as a result of changes to the protocol will be documented as an amendment to this SAP. Other than transformations or modeling needed to address the structure and distribution of the resulting data, additional analyses will be for exploratory purposes only.

The changes from the protocol specified analyses are:

1. Growth Hormone Binding Protein (GHBP) and Acid Labile Subunits (ALS) will be summarized but not analyzed as secondary endpoints.
2. Inclusion of Levine's test for homogeneity of variance
3. Inclusion of Welch's t-test if there is unequal variance
4. Replaced multiple imputation for missing data with tipping point analysis

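### The primary non-inferiority test is chosen by a Levene pre-test; at 3:1 allocation this misses the 2.5% level modestly if arm variances differ, and one ANCOVA with arm-specific variances would avoid it cheaply

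*SAP*

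**What the plan says.** SAP 6.11.1 specifies an ANCOVA with treatment, region and gender as fixed effects and baseline age, IGF-I SDS and height as covariates. No arm-specific variance is mentioned, so one pooled residual variance is implied. It continues: "Levene's will be used to determine if the variances is equal between the two treatment groups", and then "If there is evidence of unequal variance, a Welch test on the treatment main effects will be performed", with the same null at -2 cm. Of that null it says: "Rejection of this null hypothesis will be evidence of non-inferiority of somavaratan to daily rGH".

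SAP 5.3 reads differently: "The adjusted (least squares) mean and SE (standard error) from an analysis of covariance will be used to determine non-inferiority". SAP 6.2 lists the change from the protocol as "Inclusion of Welch's t-test if there is unequal variance", which suggests an unadjusted two-sample test, whereas 6.11.1 speaks of treatment main effects. Four things are left open: the Levene significance level, whether Levene uses raw values or residuals, whether Welch is covariate-adjusted, and whether it replaces the ANCOVA. Replacement is the natural reading, but neither section says so.

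On the level, SAP 3.5 has "an alpha of 0.05 (one-tailed 0.025) and a non-inferiority limit for difference in mean height velocity of 2.0 cm/yr". Protocol 9.2 has a one-sided test with alpha 0.05. SAP Section 1 says that "the analyses in the SAP supersede those in the protocol", so 2.5% is the reference level here. On size, SAP 3.5 plans 57 + 19 = 76 and enrols 84; of the upper limit it says: "Assuming the SD (standard deviation) is not greater than 3.5, the sample size should be no greater than 136 subjects".

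**The concern.** When one arm is three times the size of the other, a pooled-variance standard error is too small if the smaller arm is the more variable, and too large if it is the less variable. A variance pre-test protects only when it fires, and with 19 to 34 controls it has little power against moderate inequality. The trial would then mostly keep the pooled ANCOVA in the cases where its standard error is wrong.

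At stake is the error rate of the pivotal claim. If daily rhGH is the more variable arm, false non-inferiority exceeds 2.5%. If somavaratan is the more variable arm, power is lost. The open details also mean that two analysts could reach different conclusions from the same data while both following the SAP.

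**Working it through.** **1. The plan's own figure, and the level it implies.** Inputs (SAP 3.5): margin 2.0, SD 3.0, ratio 3:1. Assumed: true difference 0 and 80% power, which the documents do not state. Controls = (z_alpha + z_beta)^2 x 9 x (1 + 1/3) / 4.
- One-sided 5%: (1.645 + 0.842)^2 x 3 = 18.6, so 19 controls and 76 in total. This matches the plan.
- One-tailed 2.5%: (1.960 + 0.842)^2 x 3 = 23.6, so 24 controls and 96 in total. At 2.5%, 76 subjects give 71.1% power.

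The two alpha statements need reconciling, but that is a separate point. The pattern below also appears at one-sided 5% (step 5).

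**2. Pooled ANCOVA alone, closed form.** Let r = SD(rhGH)/SD(somavaratan), with m controls and 3m on somavaratan. In units of the somavaratan variance, the expected pooled variance of the difference is (3 + r^2)/(3m) and the true variance is (1 + 3r^2)/(3m). Their ratio is (3 + r^2)/(1 + 3r^2). Type I error is P(Z > 1.96 x square root of that ratio).
- r = 1.25: ratio 0.802, error 3.96%
- r = 1.5: ratio 0.677, error 5.34%
- r = 0.667: ratio 1.476, error 0.86%

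**3. The planned rule at N=84 (63 v 21), simulated.** Assumptions: normal errors, complete data, covariate R-squared 0.3, allocation-weighted mean variance 9, Levene at 5%, and Welch decides when Levene fires. Entries are percentages. Paired values are unadjusted / adjusted Welch. Error is at a true difference of -2, power at 0. Monte Carlo SE is about 0.1 point for error and 0.3-0.5 for power.

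| More variable arm | Levene fires | ANCOVA alone, error | Planned rule, error | Arm-specific ANCOVA, error | Planned rule, power | Arm-specific ANCOVA, power |
|---|---|---|---|---|---|---|
| rhGH, 1.5x | 34 | 5.2 | 4.1 / 3.7 | 2.6 | 59.1 / 59.3 | 54.7 |
| rhGH, 1.25x | 14 | 3.8 | 3.5 / 3.4 | 2.5 | 66.4 / 66.6 | 61.0 |
| equal | 5 | 2.5 | 2.6 / 2.6 | 2.5 | 71.6 / 72.0 | 70.7 |
| somavaratan, 1.25x | 11 | 1.4 | 1.8 / 1.8 | 2.4 | 74.1 / 76.1 | 79.9 |
| somavaratan, 1.5x | 24 | 1.0 | 1.6 / 2.0 | 2.6 | 74.8 / 80.2 | 84.6 |

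In the same row order, the planned rule's error at N=76 is 4.2/3.7, 3.6/3.4, 2.6/2.6, 1.8/2.0 and 1.6/1.9. At N=136 it is 3.7/3.0, 3.4/3.2, 2.4/2.5, 1.9/2.0 and 1.6/2.1. Arm-specific ANCOVA stays at 2.4-2.7% throughout.

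**4. Second set-up.** This used stratified 3:1 blocks of 4 (block size assumed), R-squared 0.25 and 80,000 null trials per setting. With rhGH 1.25-1.5 times more variable, the rule gives 3.3-3.9% at N=76-84 and 2.6-3.4% at N=136. At SDs 2.4/3.4 (somavaratan/rhGH) Levene fires in 30-41% of trials at N=84 and 44-62% at N=136; when it misses, ANCOVA's error is 5.0-5.2%. At ratio 2 and N=136 Levene fires in 93-99% of trials and the excess is gone (2.0-2.5%). With somavaratan the more variable arm, error is 1.2-2.2%.

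**5. Sensitivity.** In the second set-up at ratios 1.25-1.5, Levene at 10% gives 3.1-3.5% (N=76-84) and 2.4-3.1% (N=136). At nominal one-sided 5% the rule gives 6.0-6.8% (N=76-84) and 5.0-6.1% (N=136), against 4.9-5.2% for arm-specific variances.

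**6. Is the power difference real?** At N=76 with rhGH more variable, nominal power for the rule against arm-specific ANCOVA is 61.9/62.4% v 56.4% (1.25x) and 55.6/55.0% v 49.9% (1.5x). When each test is recalibrated to a true 2.5%, the figures are 55.7/56.6% v 56.3% and 45.1/46.4% v 48.1%. The rule's apparent advantage comes from its inflated error.

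**The case against.** The sponsor has already pre-specified protection against unequal variance, and it helps: with rhGH 1.25-1.5 times more variable, ANCOVA alone would run at about 4-5%. A reader might infer that the gate or the Welch branch causes the error and should be struck out. The documents do not support that. The error comes from the pooled ANCOVA kept when Levene misses, so removing the gate and keeping that ANCOVA would be worse.

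A reader might also infer that the trial's error rate is inflated as planned. That does not follow. SAP 3.5 and Protocol 9.2 give a single SD for both arms, nothing establishes which arm varies more, and with equal SDs the level holds. With somavaratan the more variable arm, the rule is conservative.

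Two limits on the remedy also stand. First, a power cost of at most about 2 points cannot be claimed without condition; step 6 shows 5-6 points of nominal power when rhGH is the more variable arm. Second, control near 2.5% was shown only for complete normal data, whereas SAP 6.4 imputes no growth after the last height. One check assumed mean velocity 10 cm/yr, 10% drop-out in both arms with the last height equally likely at Months 1, 3, 6 or 9, no covariates, and Welch as the arm-specific test. It gave 1.8-2.0% at equal SDs, 1.6-1.7% at 3.0/2.0 and 2.2-2.3% at 2.4/3.4. The planned rule gave 1.7% at 3.0/2.0 and 2.8-3.2% at 2.4/3.4. In that check the remedy erred on the safe side, and the planned rule's excess was smaller.

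**Conclusion.** The point holds as a modest, conditional weakness plus an under-specified decision rule. On complete normal data with Levene at 5% and Welch deciding when it fires, one-tailed error against a nominal 2.5% is:
- about 3.3-4.2% at N=76-84 and 2.6-3.7% at N=136, if the rhGH SD is 1.25-1.5 times larger;
- about 1.2-2.3%, with lost power, if somavaratan is the more variable arm;
- about 2.4-2.6% if the SDs are equal.

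The SD ratio, covariate R-squared, Levene level and normality are assumptions; the documents give none of them. If the ANCOVA governs regardless of Levene, as 5.3 could be read, the error at ratios 1.25-1.5 is about 4-5%. This should be changed because the change is cheap. It is not a flaw that invalidates the trial.

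**What to change.** Make one analysis primary whatever the observed variances, in SAP 6.11.1, and align 5.3 and 6.2 with it. Suggested text: *Non-inferiority is concluded if the lower limit of the two-sided 95% CI for the adjusted difference (somavaratan minus daily rhGH) is above -2.0 cm/yr, from the ANCOVA of Section 6.11.1 fitted with a separate residual variance for each treatment group and Satterthwaite degrees of freedom. Levene's and Welch's tests are reported as sensitivity results and do not change the conclusion.*

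The change is one sentence and one model option; Protocol 10.10 allows documented SAP changes before database lock. With equal variances the power cost against the planned rule is 0 to 1.8 points in the second set-up and 0.9-1.3 points in the N=84 table. If rhGH is moderately more variable at N=76-84, nominal power falls by up to about 5-6 points, because the rule's extra power there comes from excess error. If somavaratan is 1.25-1.5 times more variable, power at N=84 rises by about 4 to 10 points.

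Do not simply drop the gate and keep the pooled ANCOVA. If the gate is kept, state that Welch decides, the Levene level, raw or residual data, and adjusted or unadjusted Welch. That removes the ambiguity but not the excess error.
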